5.3.4 Home Use of the Study System

- After training on the study system has been completed, participants will proceed with home use
- 764 (meaning free-living use at school, home, etc.) of the study pump.
- Parents may use available manufacturer-provided software and features of the study CGM related
- to mobile data access or remote monitoring, but will be instructed not to use any third-party
- 767 components for this purpose.

768 5.3.5 Study Device Download

- Parents will be instructed to download the study CGM and pump and ketone meter prior to each
- phone or videoconference contact or on at least an every 4-week basis throughout the remainder
- of the study.

5.3.6 3-Day Phone Contact

- For participants who were on MDI at the time of enrollment, study staff will perform a phone call
- or videoconference with the parent within 3 (± 2) days following initiation of study pump use.
- 775 The following will occur:
- Assessment of compliance with study device use by review of any available device data
- Assessment of adverse events, adverse device effects, and device issues
- Study staff will answer any questions related to device use and follow the procedure for insulin pump optimization described above using the study CGM available data from the previous two weeks.

5.3.7 1-Week Phone Contact

- Study staff will perform a phone call/videoconference with the parent within 7 (± 2) days following
- 783 randomization.

785

- 784 The following will occur:
 - Assessment of compliance with study device use by review of any available device data
- Assessment of adverse events, adverse device effects, and device issues
- Study staff will answer any questions related to device use and follow the procedure for insulin pump optimization described above using the study CGM available data from the previous two weeks.

790 **5.3.8 2-Week Visit**

- Participants will have a follow-up visit 14 (\pm 4) days from the date of randomization.
- The parent will be offered review training to address any questions on the use of the study device
- 793 including meal bolus strategies and strategies related to pump use and exercise.
- 794 The following will occur:
- Assessment of compliance with study device use by review of any available device data
- Assessment of adverse events, adverse device effects, and device issues

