5.5.2 Phone Contacts

- A follow-up phone call or videoconference will occur at 10 weeks (± 7 days). At the discretion of
- the investigator, this scheduled phone contact may be replaced by an in-clinic visit.
- The following procedures are performed in both treatment groups:
- Review of available CGM, ketone meter, and/or system data to identify any safety issues associated with current insulin therapy and diabetes management approach
 - Assessment of adverse events, adverse device effects, and device issues
- Additional phone contacts may be performed as needed.

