11.5 Prophylactic Medications, Treatments, and Procedures

1477

1478

1479 11.6 Rescue Medications, Treatments, and Procedures

- All participants will be required to have a commercially available glucagon (or glucagon analog)
- preparation for treatment as needed of severe hypoglycemia.
- 1482 11.7 Participant Compensation
- Participant compensation will be specified in the informed consent form.
- 1484 11.8 Participant Withdrawal
- Participation in the study is voluntary, and a participant may withdraw at any time. For participants
- who withdraw, their data will be used up until the time of withdrawal.
- 1487 11.9 Confidentiality
- 1488 For security and confidentiality purposes, participants will be assigned an identifier that will be
- used instead of their name. Protected health information gathered for this study will be shared
- with the coordinating center, the Jaeb Center for Health Research in Tampa, FL. De-identified
- participant information may also be provided to research sites involved in the study.

1493

1494

1495

1496

1502

1503 1504

1505

1506

1507

1508

1509

1510

1511

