165	• Baseline : CGM data to calculate baseline metrics will either come from the run-in period,
166	or from the participant's personal CGM device if the run-in is not necessary:
167	• If an enrolled participant is currently using a Dexcom G5 or G6 with CGM data
168	captured on at least 11 out of the 14 days prior to enrollment, then he/she can
169	proceed directly to randomization.
170	\circ Otherwise, the participant will need to go through 2-6 weeks of run-in that includes
171	CGM use, prior to randomization.
172	\circ In either case, the last 2 weeks of CGM data prior to randomization will be used in
173	the calculation of baseline CGM metrics. If <168 hours of CGM data are available
174	for any reason (e.g., lost data or device failure), then the baseline metrics will not be
175	calculated and will be set to missing.
176	• Follow-up :
177	• CGM metrics will be calculated by pooling all CGM readings in the 13-week period
178	starting from the fourth day after the randomization visit up through the 13-week
179	visit. If a participant drops out before completing the 13-week visit, all available data
180	through the last visit date will be included for calculating CGM metrics. Minimum
181	168 hours of CGM data will be required to calculate CGM metrics.
182	• A separate set of CGM metrics will be calculated by excluding the first two weeks of
183	CGM data following the randomization visit for a sensitivity analysis with ≥ 168
184	hours of CGM data required.
185	• All CGM metrics at baseline and follow-up will be calculated giving equal weight to each
186	sensor reading for each participant.
187	• HIGH and LOW values from the sensor will be imputed as 401 and 39, respectively.
188	
189	5.4. Calculation of Insulin Metrics
190	Insulin metrics describe the seven days prior to the visit.
191	• Baseline insulin metrics will use data reported from the Diabetes Screening CRF.
192	• Insulin metrics will be calculated at 13 weeks using Tandem pump data where available,
193	otherwise using data reported on the CRF.
194	• If pump data are available, insulin metrics will be calculated from the pump data
195	using data in the 7 days prior to the visit. Insulin data on 5 of 7 days will be
196	required to calculate insulin metrics.
197	
198	5.5. Questionnaires
199	All questionnaires will be scored according to the instructions given in the reference
200	manual/documentation for the questionnaire. In case no manual exists for a given questionnaire

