- 398 For DKA and SH events, if enough events (i.e., at least 5 events combined over both treatment groups) for each outcome, the rates will be compared between the two treatment arms during the 399 400 main study phase using a robust Poisson regression. The regression will adjust for the participant-reported number of SH events 12 months prior to the start of the study and clinical 401 center as random effect. If one of the treatment groups has zero events then a Poisson model will 402 not converge and Barnard's exact test will be used instead. The amount of follow-up will be 403 included as an offset covariate to compare the rates. A similar analysis will be done for DKA, if 404 at least 5 total DKA events among both treatment groups. 405
- 406 9. Intervention Adherence

407 Closed Loop System

395

396 397

The amount of closed loop system use for the CLC group will be calculated from downloaded data over the period from the fourth day after randomization until the day before the 13-week

409 data over the period from the fourth day after randomization until the day before the 15-week410 visit. Any dropouts will be included prior to the time of dropout and their percentage will be

- 410 visit. Any diopodis will be mere 411 prorated accordingly.
- Time in closed loop overall.
- Time in closed loop by 4-week periods: Starting from the fourth day after the
 randomization visit, percent time in closed loop will be calculated within each 4-week
 period (Week 1-4, Week 5-8, and Week 9-13). The 13-week visit date will be used as end
 date of the Week 9-13 period.
- Percent time in different operational modes overall and by 4-week periods (the last interval will contain Weeks 9-13) will be tabulated and boxplots will be created by these 4-week periods.
- 420 Sensor Use

The amount of CGM sensor use for both treatment groups will be calculated from downloadeddata in the same way as closed-loop system use described above.

423 Percent time sensor use overall will be tabulated by treatment group and boxplots will be created.

424 **10. Protocol Adherence and Retention**

- The following tabulations and analyses will be performed by treatment group to assess protocol adherence for the study:
- Number of protocol and procedural deviations
- Flow chart accounting for all enrolled participants up to randomization
- Flow chart of all randomized participants at all scheduled visits and phone contacts post treatment initiation

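### SAP 5.3 ends a dropout's CGM data at the last visit, while Protocol 11.8 and SAP 9 run to withdrawal or dropout; a leaver who skips the end-of-study visit can lose uploaded data

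*SAP*

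**What the plan says.** - **SAP 5.3, Follow-up.** CGM readings are pooled "starting from the fourth day after the randomization visit up through the 13-week" visit. For a child who drops out earlier, available data "through the last visit date will be included for calculating CGM metrics". A minimum of "168 hours of CGM data will be required to calculate CGM metrics".
- **Protocol 11.8.** For participants who withdraw, "their data will be used up until the time of withdrawal".
- **SAP 9.** For closed-loop use, and by reference for sensor use: "Any dropouts will be included prior to the time of dropout and their percentage will be" prorated.
- **SAP section 2.** The SAP declares itself consistent with protocol version 11.0 apart from four listed items. The dropout cut-off is not among them.
- **Contacts.** Protocol Table 3 has visits at weeks 2, 6 and 13, in clinic or by videoconference. For week 10, Protocol 5.5.2 says: "A follow-up phone call or videoconference will occur at 10 weeks". The investigator may replace that contact with a clinic visit.
- **Leaving early.** Protocol 5.6 asks families to attend an end-of-study visit on withdrawal. It does not ask for a data upload if they do not come.
- **Uploads.** CLC families are told to download before each phone or video contact or at least every 4 weeks (Protocol 5.3.5). SC families upload before the early contacts and then at least every 4 weeks (5.4.1, 5.4.3). Staff review available CGM data at week 10 (5.5.2).

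**The concern.** Three passages give three descriptions of where a leaver's data end: last visit, withdrawal, dropout. Time in range and closed-loop use for the same child could therefore cover different periods, and the SAP does not say which contacts count as a visit. Followed literally, the SAP 5.3 rule excludes readings that staff may already have received and reviewed.

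The rule defines the primary outcome and the four hierarchical CGM outcomes (above 250 mg/dL, mean glucose, below 70 and below 54 mg/dL). A shortened record with at least 168 hours counts as observed. Multiple imputation, the pattern-mixture analysis (SAP 6.3) and the tipping-point shifts (SAP 17.1) act only on imputed values, so they leave that child's value as it is. The other CGM sensitivity analyses in SAP 6.3 change the start of the window or add data from children waiting for extension equipment. No planned analysis tests the cut-off.

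**Working it through.** **The plan's own figures.** With 60 and 30 evaluable children, SD 10 points, difference 7.5 points and two-sided alpha 0.05 (SAP 4), power is 0.918 by the normal approximation and 0.913 by the noncentral t, in line with the stated 90%. For 10% attrition, 90/0.9 = 100, or 67 + 34 = 101 with each arm rounded up; the plan has 102. None of this depends on the cut-off. The documents give no figure for the share of a dropout's data that is lost.

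**Inputs.** The window opens on Day 4 (SAP 5.3). Nominal contact days are 14, 42, 70 (phone) and 91, with windows of 4 days either side at week 2 and 7 days at the later contacts (Protocol Table 3). V is the day of the last visit and L the day of leaving. CGM data are assumed to run through Day L.

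**Formula.** Days 4 to L number L − 3, and the days after V number L − V. Share excluded = (L − V)/(L − 3).

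| Last visit V | Leaves L | Excluded | Share |
|---|---|---|---|
| 42 (week 6) | 49 | 7/46 | 15% |
| 42 | 63 | 21/60 | 35% |
| 42 | 70 | 28/67 | 42% |
| 42 | 84 | 42/81 | 52% |
| 42 | 90 | 48/87 | 55% |
| 70 (week 10 counted as a visit) | 77 | 7/74 | 9% |
| 70 | 84 | 14/81 | 17% |
| 70 | 90 | 20/87 | 23% |
| 14 (week 2) | 41 | 27/38 | 71% |
| end-of-study visit on day of leaving | any | 0 | 0% |

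Using the visit windows, a week-6 visit on Day 49 with leaving on Day 90 gives 41/87 = 47%. A Day-35 visit with leaving on Day 97 gives 62/94 = 66%.

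**How much is in hand.** The last scheduled upload prompt before week 13 is the week-10 contact, and a 4-weekly upload from then is due only by Day 70 + 28 = 98. The 28/67 figure therefore describes data likely to have been received. The Day-84 and Day-90 rows need a later upload. If the last upload was on Day 70, the loss of data in hand stays at 28 of 67 days, however much later the child leaves.

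**Leaving before the 2-week visit.** With no end-of-study visit, the last visit is randomization (Day 0), before the window opens. A child leaving on Day 13 has Days 4 to 13, which is 10 days or up to 240 hours. That exceeds 168 hours, yet none is kept and the outcome is set to missing.

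**Effect on an arm mean (assumed inputs).** Shift = share of the arm dropping out × change in each such child's time in range. With 5% and 2 points, 0.05 × 2 = 0.1 point. With 10% and 10 points, 0.10 × 10 = 1.0 point. The rule applies to both arms, so the treatment difference moves by the net of the two shifts.

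**The case against.** The term is undefined, and its natural meaning could include the Protocol 5.6 visit, which falls at or near withdrawal. On that reading SAP 5.3 and Protocol 11.8 nearly coincide and nothing is lost. The week-10 contact may become a clinic visit, scheduled visits may be held by videoconference, and unscheduled visits are allowed. Protocol 11.8 is a general statement in a miscellaneous chapter; the protocol's own CGM section (12.4.3) has no dropout rule, so SAP 5.3 fills a gap. SAP 9 is descriptive. Data never uploaded cannot be recovered under any rule. Children set to missing stay in the direct-likelihood model and are covered by the missing-data analyses.

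Most of this stands, and it limits the size. A reader might infer that the plan discards about half of any late leaver's data. The documents do not support that: it requires leaving close to week 13, missing the end-of-study visit, having no visit after week 6, and having uploaded the later data.

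It does not remove the inconsistency. Families are only asked to attend the final visit. Protocol Table 3 and SAP 10 separate visits from phone contacts, so the plainest reading leaves week 10 out. SAP section 2 claims consistency with the protocol. The missing-data analyses do not reach a shortened record that counts as observed.

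**Conclusion.** The inconsistency is real and undeclared, and its effect is conditional. If the end-of-study visit is missed and week 10 is not a visit, the rule excludes 42% of the recorded days of a child leaving on Day 70 after a Day-42 visit, and up to 55% at nominal visit days if later data were uploaded. Relative losses can be larger for early leavers, and a child leaving before the 2-week visit can lose everything despite having 168 hours. The loss is zero if the end-of-study visit is attended on leaving, and at most about 23% at nominal days for those leaving after a week-10 contact that counts as a visit.

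The shift in an arm mean, 0.1 to 1.0 point, rests on assumed dropout of 5–10% and an assumed change of 2–10 points per affected child. The trial's conclusion is unlikely to turn on it. A reader might also infer that the excluded days are those of worst control, so that the primary estimate is biased in a known direction. The documents give no data on this, and children who stop the device are encouraged to remain to the final visit (Protocol 10.6.1). This is a low-cost correction to an endpoint definition.

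**What to change.** 1. In SAP 5.3, replace the last-visit cut-off with: *through the date of withdrawal or, if lost to follow-up, the last available study CGM reading, and no later than the 13-week visit*. State which day stands for that visit (the target is Day 91) in a child who never attends it.
2. Use the same dropout end date for the closed-loop and sensor-use percentages in SAP 9.
3. In Protocol 5.6, request a final CGM and pump upload at withdrawal, done remotely if there is no visit.

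If the sponsor prefers to keep a visit-based cut-off, SAP 5.3 should say whether the end-of-study visit, videoconferences and the week-10 contact count, and SAP section 2 should list the difference from the protocol.

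The cost is a few sentences across the two documents. Uploads are already part of the schedule. The one drawback is that an end date must be assigned for children lost to follow-up, and that rule should be fixed before the outcome data are seen.

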12.3 Sample Size

Based on data from the DCLP5 study mentioned above, we conservatively estimate the standard deviation (SD) for the primary outcome, time in range (TIR), to be 10%. A sample size of N=90 subjects (60 in the CLC arm and 30 in the SC arm) therefore will give 90% power to detect a 7.5% improvement in TIR with a two-sided test and type 1 error of 5%. Accounting for potential attrition rate of up to 10%, the total sample size for the PEDAP Study is estimated at $\underline{N=102}$.

15121513

1514

The following table shows the minimum detectable difference with a total sample size N=90 for key secondary outcomes. The observed standard deviations are taken from the DCLP5 study.

Standard Deviation			Correlation		Detectable	
Outcome	CLC (n=78)	SC (N=22)	Pooled (N=100)	with Baseline	Effective SD ^a	Difference with N=90 b
$\%$ >250 mg/dL $^{\rm c}$	5.5%	9.9%	6.5%	0.69	4.7%	3.4%
Mean Glucose d	18	26	20	0.68	14	10
HbA1c	0.8%	0.9%	0.8%	0.70	0.6%	0.4%
$\%$ <70 mg/dL $^{\rm c}$	1.07%	1.13%	1.08%	0.61	0.86%	0.63%
% <54 mg/dL °	0.23%	0.23%	0.23%	0.54	0.19%	0.14%

a – After accounting for the baseline value as a covariate in the regression model.

¹⁵¹⁶ b – With 90% power and two-sided type 1 error rate = 5%.

¹⁵¹⁷ c – Outcomes with a skewed distribution winsorized at the 10th and 90th percentiles.

¹⁵¹⁸ d – Units for mean glucose are mg/dL.

- 1519 **12.4 Efficacy Outcome Measures**
- 1520 **12.4.1 Primary Efficacy Endpoint**
- CGM-measured % in range 70-180 mg/dL
- 1522 **12.4.2 Secondary Efficacy Endpoints**
- 1523 12.4.2.1 Secondary Efficacy Endpoints Included in Hierarchical Analysis
- 1524 The following secondary endpoints will be tested in a hierarchical fashion as described in
- 1525 section 12.7.1.
- CGM-measured % above 250 mg/dL
- CGM-measured mean glucose
- 1528 HbA1c at 13 weeks
- CGM-measured % below 70 mg/dL
- CGM-measured % below 54 mg/dL
- 1531 12.4.2.2 Other Secondary Efficacy Endpoints
- 1532 The following endpoints are considered exploratory. Type 1 error for these endpoints will be
- 1533 controlled using the false discovery rate (FDR) instead of the familywise error rate (FWER).
- 1534 *CGM-Measured*:
- 1535 % above 180 mg/dL
- 1536 % in range 70-140 mg/dL
- glucose variability measured with the coefficient of variation (CV)
- glucose variability measured with the standard deviation (SD)
- 1539 % <60 mg/dL
- low blood glucose index (LBGI)*
- hypoglycemic events (defined as at least 15 consecutive minutes <54 mg/dL)

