Précis	A randomized controlled trial of at-home closed loop system vs. standard care (defined as either multiple daily injections of insulin [MDI] or use of an insulin pump without hybrid closed-loop control capabilities [low-glucose suspend or predictive low-glucose suspend functionality is permitted]) in youth age 2 to <6 years old.
Investigational Device	t:slim X2 with Control-IQ and Dexcom G6 system
Objectives	The objective of the study is to assess efficacy, quality of life, and safety of a closed loop control (CLC) system (t:slim X2 with Control-IQ Technology) in a randomized controlled trial with partial crossover.
Study Design ¹	First phase: a 13-week parallel group randomized clinical trial with 2:1 randomization to intervention with the closed loop system vs. standard care (SC); Second Phase: following the RCT, a 13-week period where the Standard Care (SC) group will transition to use CLC and the experimental arm will extend the use of CLC for the same period. After 26 weeks, participants may continue using CLC for an additional Extended Use period. A subset of participants will be invited to join an optional exercise/meal challenge ancillary study.
Number of Clinical Centers	~3 US clinical centers
Endpoints	Efficacy The primary outcome for the RCT is time in target range 70-180 mg/dL (TIR) measured by CGM in CLC group vs. SC group over 13 weeks The primary outcome for the extension phase assessed separately for each treatment group is change in TIR comparing extension phase with RCT phase.
	Quality of Life Patient-reported outcome questionnaires will be completed. Safety The key safety outcomes are severe hypoglycemia and ketoacidosis.
Population	 Inclusion Criteria Clinical diagnosis, based on investigator assessment, of type 1 diabetes for at least 6 months and using insulin for at least 6 months Familiarity and use of a carbohydrate ratio for meal boluses. Age ≥2 and <6 years old Living with one or more parent/legal guardian knowledgeable about emergency procedures for severe hypoglycemia and able to contact emergency services and study staff. Investigator has confidence that the parent can successfully operate all study devices and is capable of adhering to the protocol Willingness to switch to lispro (Humalog) or aspart (Novolog) if not using already, and to use no other insulin besides lispro (Humalog)

PARTICIPANT AREA	DESCRIPTION

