- Number of and reasons for unscheduled visits and contacts
- Number of participants who stopped treatment and reasons
- 433

434 11. Baseline Descriptive Statistics

- Baseline demographic and clinical characteristics of the cohort of all randomized participants
 will be summarized in a table using summary statistics appropriate to the distribution of each
- 437 variable. Descriptive statistics will be displayed by treatment group for the following:
- 438
- 439 Age
- 440 Gender
- Race/ethnicity
- Parent's income, education, and/or insurance status
- Diabetes duration
- Insulin method before enrollment (pump vs. MDI)
- CGM use before enrollment
- 446 HbA1c
- 447 BMI %
- Participant-reported number of SH and DKA 12 months prior to the start of the study
- Baseline CGM metrics including:
 - \circ % in range 70-180 mg/dL
 - \circ % time >250 mg/dL
- 452 o Mean glucose
 - \circ % time <70 mg/dL
- 454 \circ % time <54 mg/dL
- 455

450

451

453

456 12. Device Issues

- 457 The following tabulations and analyses will be performed by treatment group to assess device458 issues:
- Device malfunctions requiring study team contact and other reported device issues
- Rate of different failure events and alarms per 24 hours recorded by the Control-IQ
 system overall and by month
- 462

463 **13. Planned Interim Analyses**

- 464 No formal interim efficacy analyses are planned. The analysis of the RCT will be performed on465 completion of the RCT prior to the completion of the extension phase.
- 466
- 467 The DSMB will review safety data at intervals, with no formal stopping rules.
- 468

469 **14. Subgroup Analyses**

In exploratory analyses, the primary outcome (% time 70-180 mg/dL), % time <70 mg/dL and
HbA1c at 13 weeks will be assessed separately in various subgroups. Subgroups will be defined

according to the baseline value of the factors listed below. Statistical analysis will involve tests 472

for interaction with treatment group. 473

Interpretation of subgroup analyses will be viewed with caution, particularly in the absence of an 474

overall significant difference. For continuous variables, results will be displayed in subgroups 475

based on cutpoints although the analysis will utilize the variable as continuous, except for age 476

- 477 which will be analyzed both as a continuous variable and in two age groups. If there is
- insufficient sample size in a given subgroup, the cutpoints for continuous measures may be 478

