- adjusted per the observed distribution of values. Cutpoint selection for display purposes will be 479 made masked to the outcome data.
- 480
- Age (≤ 4 vs. ≥ 4) 481 •
- Gender 482
- Race/Ethnicity 483
- Parent's income, education, and/or insurance status 484
- Diabetes duration 485
- Insulin method before enrollment (pump vs MDI) 486
- CGM use before enrollment 487
- Baseline HbA1c 488
- 489 • Body mass index (%)
- Participant-reported number of SH and DKA 12 months prior to the start of the study 490
- Clinical center (test for random effects interaction with treatment group) 491
- Baseline CGM metrics including: 492
 - % time in range 70-180 mg/dL
 - \circ % time >250 mg/dL
 - Mean glucose
 - \circ % time <70 mg/dL
 - \circ % time <54 mg/dL
- The p-value for any categorical variable will only be calculated if there are a minimum of 498 10 participants per treatment group. 499
- 500 501

493

494

495

496

497

- 502 **15. Multiple Comparisons**
- 503 Hierarchical Analyses

The hierarchical testing procedure described above will be used to control the overall type 1 504 error for the primary outcome plus five key secondary outcomes identified above. 505

All Other Secondary Analyses 506

For comparison of all other efficacy endpoints, the false discovery rate (FDR) will be controlled 507 using the adaptive Benjamini-Hochberg method adapted using the two-stage test. FDR adjusted 508 p-values will be calculated separately for the following categories: 509

- All other CGM metrics 510
- HbA1c analyses 511
- Insulin, weight, and BMI 512
- Questionnaires 513

- Subgroup analyses for % time 70-180 mg/dL and HbA1c at 13 weeks
 Subgroup analyses for % time < 70 mg/dL
 P-values from safety analyses, sensitivity analyses and per-protocol analyses will not be adjusted
- 518 for multiple comparisons.
- 519
- 520

521 16. Exploratory Analyses

522 CGM Metrics

- 523 In addition to the analysis for the hierarchical CGM-measured endpoints described earlier, 524 separate analyses will be conducted with the appropriate statistics for daytime (6:00am –
- 525 9:59pm) and nighttime (10:00 PM 5:59 AM) separately. No p-values will be calculated for
- following analyses. (10.00 PM 5.59 AM) separately. No p-values will be calculated for following analyses.
- 527 % time in range 70-180 mg/dL
- Mean glucose
- % above 250 mg/dL
- 530 % below 70 mg/dL
 - Coefficient of variation
- 531 532

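### SAP 14 tests center-by-treatment heterogeneity as a random-effects interaction with about 3 centers and names no statistic; the usual variance-component tests are conservative there, and a fixed 2-df test is better calibrated.

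*SAP*

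**What the plan says.** SAP section 14 (Subgroup Analyses) lists the baseline factors to be examined for interaction with treatment. For center, and only for center, it specifies the kind of test: "Clinical center (test for random effects interaction with treatment group"). The SAP synopsis puts the number of centers at about "3 US clinical centers". Neither document says whether the test is a likelihood-ratio, Wald or F test, which reference distribution applies, or how the random effects are set up.

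The section is labelled exploratory ("In exploratory analyses, the primary outcome (% time 70-180 mg/dL), % time <70 mg/dL and" HbA1c are the outcomes), and it warns that "Interpretation of subgroup analyses will be viewed with caution". SAP section 15 controls the false discovery rate for subgroup p-values. Section 14 also withholds the p-value for a categorical factor unless there are at least 10 participants per treatment group. It does not say whether that means overall or within each level of the factor.

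Center is the only stratification factor (Protocol 4.1.1). Enrollment per center is not capped (Protocol 1.4 and 2.1).

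**The concern.** A random-effects interaction test asks whether the between-center variance of the treatment effect is zero. The usual large-sample references for such a test assume many clusters. With 3 centers there are only 2 degrees of freedom of information, and the hypothesis sits on the edge of the parameter space.

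What is at stake is the check on whether the effect is consistent across sites. That check has some interest here. Insulin adjustment follows each practice's own guidelines (Protocol 3.5 and 5.5.3), and the data may be used in regulatory submissions (Protocol 1.2). A conservative test makes a non-significant result less informative than it appears. With so few levels, the interaction can instead be tested directly as fixed contrasts.

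**Working it through.** **Inputs from the documents.** Protocol 12.3 sets the "deviation (SD) for the primary outcome, time in range (TIR), to be 10" percent, uses "60 in the CLC arm and 30 in the SC arm", and claims "90% power to detect a 7.5" percentage-point gain with a "two-sided test and type 1 error of 5" percent. The randomization target is 102 at 2:1.

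**Assumptions not in the documents.** Nominal 5% for the interaction test; 3 equal centers; residual SD of 10 or 8 after adjustment; illustrative center effects.

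**The plan's own figure.** 7.5 / (10 × √(1/60 + 1/30)) = 3.354, and Φ(3.354 − 1.960) = 0.918 (0.913 with the t distribution), against a stated 90%. Allowing for 10% attrition, 90/0.9 = 100, against a stated 102. Both reproduce closely. The documents give no size or power for the center test.

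**Size with 3 balanced centers.** Let Q be the heterogeneity statistic of the three center-specific effects, which is chi-square with 2 df under the null. The REML likelihood ratio for a random interaction is

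LR = Q − 2 − 2 ln(Q/2) for Q > 2, and 0 otherwise.

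- The variance estimate is zero with probability P(Q < 2) = 1 − e^(−1) = 63%.
- 50:50 mixture: the cut-off 2.706 corresponds to Q = 7.29, so size = e^(−7.29/2) = 2.6%.
- Chi-square with 1 df: the cut-off 3.841 corresponds to Q = 8.81, so size = e^(−8.81/2) = 1.2%.
- The fixed test rejects at Q = 5.99, with size 5%.

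A finite-sample version, with F as the fixed 2-df interaction statistic and N = 102, gives the same picture. The likelihood-ratio test needs F above 3.75 (mixture) or 4.56 (chi-square), against 3.09 for the fixed test. Its sizes are 2.7% and 1.3%. Simulations used equal and unequal centers, two parameterisations, and a center main-effect SD of 1 or 4 (assumed). They gave 1.3–3.6% (mixture), 0.4–1.7% (chi-square) and 4.5–5.4% (fixed F).

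A Wald z for the variance component is (F − 1)/√(F² + 2/(N − 6)). It stays below about 1.0 however large F is, so it never reaches 1.645 or 1.96.

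**Power for center effects of 12, 12 and 2 points, 23:11 per center.** The mean is 8.67, and the squared deviations sum to 11.11 + 11.11 + 44.44 = 66.67. The variance of one center's effect is SD² × (1/23 + 1/11) = SD² × 0.1344. The noncentrality is 66.67/13.44 = 4.96 at SD 10 and 66.67/8.60 = 7.75 at SD 8. From the noncentral chi-square with 2 df, before FDR adjustment:

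| Test | SD 10 | SD 8 |
|---|---|---|
| Fixed, 2 df | 50% | 70% |
| Likelihood ratio, 50:50 mixture | 40% | 61% |
| Likelihood ratio, chi-square 1 df | 29% | 50% |

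**Other patterns (N = 102, SD 10, F version), effects 7.5 and 7.5 ± g.**

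| g | Fixed | Mixture | Chi-square |
|---|---|---|---|
| 5 | 38% | 29% | 20% |
| 7.5 | 73% | 64% | 53% |
| 10 | 94% | 90% | 84% |

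Parameterisation matters. In simulation with effects 0/7.5/15, the fixed test has 73–74% power. A center-by-treatment cell effect gives about 67% (mixture) and 56% (chi-square). A random slope gives 73% and 64%, so with the mixture reference it loses almost nothing.

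**The case against.** **The statistic is unnamed.** A reader might infer that the SAP's test has a true size of 1–3%. The text does not support that. The figure belongs to a REML likelihood-ratio test, and the SAP could equally mean a Wald test (0%) or an exact F test of the same component (5%). In the balanced case the likelihood ratio is a monotone function of the fixed F whenever F exceeds 1. The loss therefore comes from calibration, not from treating center as random. This objection stands, and it limits the point to an unspecified test whose usual forms are conservative.

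**Little is missed.** A reader might also infer that the test overlooks site differences that a fixed test would find. That is too strong. At the protocol's SD, the fixed test detects the 12/12/2 pattern only about half the time, although that pattern needs one site to differ by 10 points, more than the 7.5-point design effect. FDR adjustment would lower the power of either test further.

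**Low consequence and partly covered.** The analysis is exploratory and flagged for caution. A random interaction matches the random center effect in the main models, which is a recognised choice. Section 14 already plans separate assessment within subgroups, so center-specific results may be intended. All of this stands, and it keeps the point minor. It does not supply the missing statistic or reference distribution.

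**Conclusion.** The point holds as a minor improvement. With about 3 centers, the usual variance-component tests are conservative: about 1.2% or 2.6% for the REML likelihood-ratio test at an assumed nominal 5%, and effectively zero for a Wald z test. Against a fixed 2-df test, the likelihood-ratio test gives up about 10 points of power (mixture) or 20 points (chi-square) in the 12/12/2 example. The loss is smaller for a random-slope form and for larger differences.

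These figures rest on three equal centers, a residual SD of 8 to 10, illustrative center effects and no FDR adjustment. The primary, hierarchical and safety analyses do not depend on this test, and nothing here suggests that they are affected.

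**What to change.** Change the clinical-center line in SAP section 14 to a fixed treatment-by-center interaction (2 df with 3 centers), reported with center-specific treatment effects and 95% confidence intervals. Center enters this one model as a fixed factor and stays random in the main models. If a random interaction is preferred, name the statistic and give it an exact or bootstrap reference.

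The cost is one line of text and one clarification: state whether the minimum of 10 per treatment group applies within each center. At 102 randomized 2:1, standard care has 34 children, about 11 per center. With uncapped enrollment, an assumed split of 51/33/18 would leave 17, 11 and 6, and a within-center rule would then suppress the p-value. The center-specific estimates and intervals should be reported in either case.
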